### **8.2.2.3 Safety evaluation set (SES)**

Consists of all patients with exposure to venetoclax.

## **8.2.3 Definition of endpoints**

### **8.2.3.1 Primary endpoint CR/CRi rate**

The CR/CRi rate is the primary endpoint of the phase II expansion part. It is determined as follows: number of patients who achieved CR or CRi, divided by the number of all patients in the analysis set.

### **8.2.3.2 Secondary Endpoints**

- Duration of remission: Time from CR/CRi until relapse, only calculated for relapsed patients.
- Cumulative incidence of relapse: Proportion of patients in CR/CRi relapsing during observational period. Death in remission is considered as competing event. Observation is censored at the end of the observational period if no relapse occurred.
- Depth of remission (MRD): Number of patients who achieved MRD negative CR/CRi, divided by all patients with MRD marker
- Overall survival: Time from date of first application of study drug until date of death. Observation is censored at the end of the observational period in case of survival.
- Early mortality: number of patients who died within 14 and 30 days from date of first study drug administration, divided by all patients in the analysis set
- Proportion of allogeneic stem cell transplantation following response: number of patients with CR/CRi who underwent allogeneic stem cell transplantation, divided by the number of all patients who achieved CR/CRi
- Tolerability: incidence and grade of adverse events

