Statistical Considerations	
The phase I part will be conducted according to the enhanced algorithms of a 3+3H design (Ji et al. J Clin Oncol 2013).
 
The phase II part will be performed as single stage study adopting the A'Hern design (A'Hern Stat Med 2001). The phase II part of the trial will test the null hypothesis that the CR/CRi rate is <math>\leq 45\%</math>. This benchmark for the CR/CRi rate was selected based on literature review of trials for this patient population. The primary efficacy analysis the CR/CRi rate will be calculated by the number of observed CR's/CRi divided by the total number of patients in the phase II full analysis set. We expect a CR/CRi rate of 65% with the combination treatment. This expectation is based on CR/CRi rates reported for the combination of venetoclax and demethylating agents in patients with de novo AML being around 70% (DiNardo ASH 2015, Pollyea ASCO 2016). The null hypothesis will be tested with the one-sample exact binomial test with a one-sided type one error probability of 5% and a power of 80%. Given 25 CR/CRis observed among the 42 patients treated at the MTD the null hypothesis will be rejected.

Anticipated Duration	
Entire Trial
 
First patient in to last patient out (months): 48 months
 
Recruitment period (months): 24 months
 
Follow-up period: 24 months after enrolment of last patient
 
Follow-up period per patient: minimum 24 months after study enrolment
 
AE reporting period: day 1 of V-MAC until 28 days after end of venetoclax treatment

Ancillary Research	
Biomarkers for response to venetoclax have not yet been established for patients with AML. Response may depend on the activation of specific intracellular signaling pathways. Identification of biomarkers might help to better interpret results from clinical trials, improve the design of future trials and to identify patient groups who benefit most from this drug. Moreover, venetoclax maintenance therapy may impact on pre-malignant clonal hematopoiesis especially when the founding clones are defined by mutations in chromatin modifiers (Shlush et al., Nature 2014 and Jeziskova et al., Int J Hematol 2015).

Therefore, we will set out to study changes in the clonal composition of hematopoiesis in patients who achieved a remission.

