#### Secondary Endpoints

- Duration of remission
- Cumulative incidence of relapse
- Depth of remission (MRD)
- Relapse-free survival
- Overall survival
- Early mortality (within 14 and 30 days)
- Proportion of allogeneic stem cell transplantation following response
- Tolerability (incidence and grade of adverse events)

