## **8.2.4 Statistical methods**

The primary endpoint will be analyzed confirmatory. All other analyses will be descriptive and exploratory.

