### 8.2.5.2 Secondary endpoints

- Duration of remission is estimated only in patients who relapse. Median and interquartile range will be presented together with the absolute number of relapsed patients and percentage based on all patients who achieved CR/CRi.
- Cumulative incidence of relapse is estimated with the competing risk methodology according to Fine and Gray (1988), death in remission is considered as competing event, cumulative incidences and two-sided 95% confidence intervals will be presented for meaningful time points.
- Depth of remission: Absolute numbers and proportion of patients with MRD negative CR/CRi and a two-sided 95% Clopper-Pearson confidence interval, separately for all planned remission control times will be presented
- Overall survival is analyzed with the Kaplan-Meier method, median overall survival time and two-sided 95% confidence interval will be estimated, proportion of surviving patients and two-sided 95% confidence intervals will be presented for meaningful time points
- Absolute numbers and proportion of patients suffering from early mortality (within 14 and 30 days) will be presented. A two-sided 95% Clopper-Pearson confidence interval for the proportion will be calculated.
- Absolute number and proportion of allogeneic stem cell transplantations following response and a two-sided 95% Clopper-Pearson confidence interval for the proportion will be calculated.

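### Duration of remission is computed only in patients who relapse, so the one remission duration reported is biased short, and the listed relapse-free survival endpoint is left undefined

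*Protocol*

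**What the plan says.** Section 8.2.3.2 gives the definition: "Duration of remission: Time from CR/CRi until relapse, only calculated for relapsed patients". Section 8.2.5.2 repeats the restriction, "Duration of remission is estimated only in patients who relapse", and fixes the summary: "Median and interquartile range will be presented together with the absolute number of relapsed patients and percentage based on all patients who achieved CR/CRi". There is no censoring rule for responders who have not relapsed.

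A second relapse endpoint is handled differently. Section 8.2.3.2 has "Cumulative incidence of relapse: Proportion of patients in CR/CRi relapsing during observational period", with death in remission competing and patients without relapse censored. Section 8.2.5.2 adds that "Cumulative incidence of relapse is estimated with the competing risk methodology", with 95% confidence intervals at selected time points.

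The synopsis and section 3.5 also list "Relapse-free survival" as a secondary endpoint. It has no entry in 8.2.3.2, where all seven other listed secondary endpoints are defined, and no analysis anywhere in section 8.2.

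On status, section 8.2.4 makes only the primary endpoint confirmatory: "All other analyses will be descriptive and exploratory". On follow-up, the synopsis states "Follow-up period per patient: minimum 24 months after study enrolment", with 24 months of recruitment and 48 months from first patient in to last patient out.

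**The concern.** Restricting a duration to patients who had the event conditions on the bad outcome. The longest remissions are the ones most likely to be still running at cut-off, and these are removed. What remains is the distribution of relapse times among relapses that happened to fall within follow-up. Three things follow:

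- The median is too short whenever some responders have not relapsed by cut-off.
- It lengthens with later cut-offs, so it cannot be compared with a series that had different follow-up.
- If treatment, maintenance or transplantation prevents relapses without delaying those that still occur, the median stays where it is.

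A valid relapse-free survival analysis would give an all-responder time with relapse and death both counted. The protocol lists that endpoint but does not say what starts the clock, what counts as an event or when a patient is censored. A reader of the trial report would then find one figure labelled duration of remission, and it would answer a different question.

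**Working it through.** The protocol states no figure for duration of remission or relapse-free survival, so there is none to reproduce on this point. The one computable design figure, 25 responses in 42 patients against 45% with 65% expected, does reproduce: exact one-sided alpha 0.0415, power 0.818. It does not depend on anything below.

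**Inputs.** From the protocol: follow-up of at least 24 months from enrolment, recruitment over 24 months, 42 patients, expected CR/CRi rate 65%. Assumed, because the protocol gives no relapse or death rates among responders: exponential time to relapse with median m from 6 to 36 months.

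**1. Fixed follow-up of T = 24 months from remission, no deaths.** The share relapsing by T is F = 1 − 2^(−T/m). The median among those who relapse is t = −m × log2(1 − F/2). For m = 12: F = 1 − 2^(−2) = 0.75, and t = −12 × log2(0.625) = 8.1. Expected responders are 42 × 0.65 = 27.3, so relapsers are 27.3 × F.

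| True median (months) | Share relapsed by 24 months | Expected relapsers of 27.3 | Reported median (months) |
|---|---|---|---|
| 6 | 0.938 | 25.6 | 5.5 |
| 12 | 0.750 | 20.5 | 8.1 |
| 18 | 0.603 | 16.5 | 9.3 |
| 24 | 0.500 | 13.7 | 10.0 |
| 36 | 0.370 | 10.1 | 10.6 |

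Doubling the true median from 12 to 24 months moves the reported figure by 1.8 months (9.96 − 8.14).

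**2. Follow-up spread evenly over 24 to 48 months from enrolment, CR assumed at 1.2 months.** Follow-up from remission then runs from 22.8 to 46.8 months. The overall share relapsing before cut-off is P = 1 − [m/(24 ln 2)] × [2^(−22.8/m) − 2^(−46.8/m)]. As long as the median falls below 22.8 months, the same formula applies with P in place of F. For m = 12: P = 0.855, and t = −12 × log2(1 − 0.4275) = 9.7. For m = 6 and m = 24, P is 0.976 and 0.626, and the readings are 5.8 and 13.0. A simulation of one million remission times per case gave the same values (5.79, 9.66, 13.01). The bias is smaller than in step 1 and has the same direction.

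**3. Fewer relapses, unchanged timing.** Let a fraction c of responders never relapse and the rest relapse with median 6 months; follow-up is 24 months. The relapsers-only median does not involve c. The all-responder median is −6 × log2(1 − 0.5/(1 − c)), and the 24-month cumulative incidence is (1 − c) × 0.9375.

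| Never relapsing | Relapsers-only median (months) | All-responder median (months) | 24-month cumulative incidence |
|---|---|---|---|
| 0% | 5.5 | 6.0 | 94% |
| 20% | 5.5 | 8.5 | 75% |
| 40% | 5.5 | 15.5 | 56% |
| 60% | 5.5 | not reached | 38% |

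**4. With death in remission.** Take relapse median 12 and death median 36 months. The hazards add, so the relapse-free survival median is 1/(1/12 + 1/36) = 9.0 months. Step 1 with m = 9 gives a relapsers-only median of 7.1 months.

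**The case against.** The best defence is that the plan does not rest on this one number. Cumulative incidence of relapse covers every responder, treats death in remission as competing, and is reported over time with confidence intervals. The percentage of responders who relapsed is printed beside the median. In the third table the last column, which the plan will report, shows the change clearly. A reader might infer that the plan has no valid time-based summary of relapse, or cannot show a benefit from fewer relapses. The documents do not support either reading.

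The size is also open. The protocol describes relapse-free survival under established regimens as short. At a true median of 6 months the error is half a month or less. Follow-up of exactly 24 months is the least favourable case that the protocol allows.

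Further, every endpoint here is exploratory, and a statistical analysis plan due before database lock could define relapse-free survival.

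Most of this stands and limits the severity. It does not remove the point. The relapsers-only restriction is a rule stated twice, not a detail left open. The cumulative incidence curve does not correct a figure labelled as a duration. Relapse-free survival is the one listed secondary endpoint left out of the section that defines all the others, and cumulative incidence does not replace it, because there death competes instead of counting as an event.

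**Conclusion.** The point holds as a should-fix. As written, duration of remission estimates time to relapse among patients who relapsed before cut-off, and it is the only remission duration the trial will report. Its direction of error is certain whenever some responders have not relapsed by cut-off and could still do so. The size depends on assumed exponential relapse: from about half a month or less at a true median of 6 months, through 2 to 4 months at 12, to 11 to 14 months at 24, across the two follow-up patterns.

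Separately, relapse-free survival is promised in the synopsis and section 3.5 and not specified in section 8.2.

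A reader might go further and conclude that the efficacy claim is compromised. It is not: the CR/CRi test, its 25-of-42 rule and the sample size do not use either endpoint, and cumulative incidence of relapse is soundly planned.

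**What to change.** In sections 8.2.3.2 and 8.2.5.2:

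- Define relapse-free survival in all CR/CRi patients as time from CR/CRi to relapse or death from any cause, censored at the last disease assessment, and estimate it by Kaplan-Meier with median and confidence interval. State how transplantation is treated in the analysis.
- Base duration of remission on all responders, with patients who have not relapsed censored and death in remission as a competing event, consistent with the cumulative incidence already planned. The two then overlap, so one curve can serve both, with the time at which it reaches 50% quoted if it does.
- Delete the relapsers-only median, or keep it under the label 'time to relapse among relapsed patients'.

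The cost is wording. Remission status and survival are already collected every 3 months for at least 24 months (Tables 9 and 10), so no new data, visits or patients are needed. The change should be made before database lock.

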## **8.2.4 Statistical methods**

The primary endpoint will be analyzed confirmatory. All other analyses will be descriptive and exploratory.

### **8.2.4.1 Descriptive statistics**

Descriptive analyses in the expansion part of the study will follow the principles as described for the phase I dose escalation study part.

#### 8.2.4.2 Missing values

Primary endpoint: The number and proportion of missing values will be reported. Missing values can occur - for example – in the following cases:

- A patient dies before remission assessment
- A patient withdraws consent before remission assessment and does not allow collection of follow-up data
- Remission assessment is not done due to other reasons (with or without withdrawal from study treatment)
- Remission assessment is done but no valid result is available (punctio sicca, etc.)

In all cases the missing outcome is treated as failure to achieve CR/CRi. This strategy is considered to be conservative, because it can only result in underestimation of efficacy, making it harder to reject the null hypothesis.

For all other endpoints and variables the number and proportion of missing values will be reported.

Even if the patient has not been treated according to protocol or has interrupted his/her study treatment prematurely, as many endpoints as possible should be assessed. Drop-out from treatment does not mean drop-out from follow-up!

#### 8.2.4.3 Center effects

In the primary analysis centers will not be taken into account. In a sensitivity analysis the proportion of CR/CRi is estimated using a generalized estimation equation (GEE) model with logit link function and a compound symmetry correlation structure to take into account the correlation of patients within a trial center. The model will include an intercept term only. The proportion of patients with CR/CRi will be derived by calculation of  $\exp(b_0)/(1+\exp(b_0))$  with  $b_0$  as the estimation of the intercept term from the GEE model.

#### 8.2.4.4 Multiplicity

The primary analysis of the primary endpoint is conducted only one time at the end of trial phase. No interim analyses are planned, no multiple comparisons are planned. Therefore no adjustment for multiple hypothesis tests is necessary. Analyses of secondary endpoints are exploratory and will therefore not be adjusted for multiplicity.

#### 8.2.5 Analysis of Efficacy

All analyses will be conducted in the full analysis set (FAS). An analysis in the per-protocol set (PPS) is conducted as sensitivity analysis.

##### 8.2.5.1 Primary endpoint, primary analysis

Absolute frequencies and proportion of patients who achieve CR/CRi will be calculated. A two sided 95% Clopper-Pearson confidence interval for the proportion will be calculated. The null

hypothesis ( $H_0: p \leq 0.45$ ) will be tested with the exact binomial test at a one-sided significance level of 5%.

### 8.2.5.2 Secondary endpoints

- Duration of remission is estimated only in patients who relapse. Median and interquartile range will be presented together with the absolute number of relapsed patients and percentage based on all patients who achieved CR/CRi.
- Cumulative incidence of relapse is estimated with the competing risk methodology according to Fine and Gray (1988), death in remission is considered as competing event, cumulative incidences and two-sided 95% confidence intervals will be presented for meaningful time points.
- Depth of remission: Absolute numbers and proportion of patients with MRD negative CR/CRi and a two-sided 95% Clopper-Pearson confidence interval, separately for all planned remission control times will be presented
- Overall survival is analyzed with the Kaplan-Meier method, median overall survival time and two-sided 95% confidence interval will be estimated, proportion of surviving patients and two-sided 95% confidence intervals will be presented for meaningful time points
- Absolute numbers and proportion of patients suffering from early mortality (within 14 and 30 days) will be presented. A two-sided 95% Clopper-Pearson confidence interval for the proportion will be calculated.
- Absolute number and proportion of allogeneic stem cell transplantations following response and a two-sided 95% Clopper-Pearson confidence interval for the proportion will be calculated.

### 8.2.6 Exploratory endpoints

Multivariable logistic regression models will be fitted to identify biological factors predicting CR/CRi achievement, adjusted odds-ratios and two-sided 95% confidence intervals will be estimated.

### 8.2.7 Analysis of Safety

#### 8.2.7.1 Extent of exposure

Extent of exposure is analyzed as described for the phase I dose escalation part of this trial (see section [8.1.5.1](#)).

#### 8.2.7.2 Adverse events

Analysis of adverse events will be conducted as described for the phase I dose escalation part of this trial (see section [8.1.5.3](#)).

### **8.2.7.3 Laboratory parameters**

Analysis of laboratory parameters will be conducted as described for the phase I dose escalation part of this trials (see section [8.1.5.4](#)).

Additionally a comparison of V1 and EOT is done for patients who received more than one treatment cycle.

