**Inclusion criteria applying for expansion phase (Phase II) only:**

- Primary refractory after 1-2 cycles of standard induction chemotherapy (100 to 200 mg/m^2 cytarabine over 7-10 days plus anthracycline or mitoxantrone over 3 days) or relapsed from first or second CR after 1-2 cycles of standard induction chemotherapy (which must have included cytarabine with an anthracycline or anthracenedione), including relapse after allogeneic stem cell transplantation

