#### 5.1.2 Packaging and labeling

The pharmaceutical manufacturer AbbVie is responsible for quality control, labelling, batch release, packaging and shipment to the central distribution pharmacy. Venetoclax will be labeled according to the requirements of local law and legislation. Label text will be approved according to the Sponsor's procedures. A complete record of batch numbers and expiry dates of all study treatment will be maintained in the sponsor study file.

The clinical trial sites will be supplied with a venetoclax supply sufficient for one full cycle of V-MAC for one patient, i.e.

- 1 blister of "**8 x 50mg tablets, child resistant blister cards**" (sufficient for days 1-3) and
- 4/6 blisters of "**8 x 100 mg tablets, child resistant blister cards**" (sufficient for days 4-10/14)

For maintenance treatment, the clinical trial sites will be supplied with 3 bottles, each containing "**120 x 100mg tablets, child resistant bottles**", re-supply every 3 months on request of trial site.

If a dose reduction of venetoclax is necessary because of co-administration of strong and/or moderate CYP3A inhibitors during the expansion phase and maintenance, the patient will be supplied with sufficient blisters of "**16 x 10mg tablets, child resistant blister cards**".

Each blister or bottle carries a label as shown in [Figure1](#), depending on the dose it contains.

TUD-RELAX1-070 (A16-332)	
Technische Universität Dresden, Medizinische Fakultät, [name], [contact]	
Prüfpräparat für durch Prüfarzt initiierte Klinische Prüfung	
EudraCT-Nummer: 2018-003025-28	
Venetoclax 50 mg Filmtablette	
Nur zur oralen Einnahme.	8 Tabletten
Name des Prüfarztes: _____	
Telefonnummer des Prüfarztes: _____	
Nach Anweisung des Prüfarztes einnehmen. Bei 15 - 25°C lagern.	
Bitte geben Sie das gebrauchte oder ungebrauchte Prüfpräparat wie mit Ihrem Prüfpersonal vereinbart wieder zurück.	
Für Kinder unzugänglich aufbewahren. Zur Klinischen Prüfung bestimmt.	
1) Kit-Nr.: XXXXXXXX	
2) Ch.-B.: XX-XXXXXX	Patientennr.: _____
3) Verwendbar bis: XX-XX-XXXX	Abgabedatum: _____

[Figure 1](#): sample of packaging label of venetoclax

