### Venetoclax

**Day 1 of venetoclax will define the study treatment start.** To mitigate the potential risk of TLS, venetoclax administration will start with a pre-specified dose ramp-up to reach the target dose level of 400 mg at day 4 (refer to Table 2).

Table 2: Venetoclax ramp up

Day	Venetoclax dose
1	50 mg
2	100 mg
3	200 mg
4 – 14 (10)*	400 mg

\* Venetoclax will be administered until day 14, only at dose level -1, venetoclax will be given until day 10.

Each dose of venetoclax should be taken with approximately 240 ml of water within 30 minutes after the completion of a meal, preferably breakfast. The dose should be administered at the same time each day. On days with planned cytarabine administration, venetoclax must be given prior to cytarabine and mitoxantrone. If a patient develops any lab changes suggestive of TLS within the first 24 hours after either first dose or during ramp up, venetoclax should be withheld until normalization of lab changes. Venetoclax will be administered in Phase I and II no longer than 10/14 days except during maintenance therapy.

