## **5.4.3 Treatment schedule in the maintenance therapy**

Patients who achieve a CR/CRp with ANC recovery ( $ANC \geq 1000/\mu L \geq 1 \times 10^9/L$ ) may receive venetoclax maintenance treatment up to twelve 28-day cycles if they have no other post-remission treatment options (e.g. auto/allo-TX, chemo-consolidation therapy etc.).

Venetoclax will be given at dose 400 mg QD per os as continuous treatment starting within 14 days after the End of Treatment assessment of previous treatment phase up to 12 cycles. Duration of one cycle is 28 days.

If co-administration with strong and moderate CYP3A inhibitors daily dose will be reduced according to section [5.5](#).

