#### 5.4.4 Dose modifications during V-MAC in expansion and maintenance treatment

The following dose reduction rules shall be applied in case toxicities occur.

In case of either one of these toxicities, venetoclax shall be stopped and re-started according to the recommended dose modifications in Table 3 and Table 4. If co-administration of strong or moderate CYP3A inhibitors, venetoclax dose modification has to be done according to [Table 5](#) and [Table 6](#).

In maintenance therapy, dose reductions according to [Table 3](#), [Table 4](#), [Table 5](#), [Table 6](#) are necessary if either one of the below occurs in patients with CRp:

- ANC falls <1000/ $\mu$ L or
- PLT count falls <50,000/ $\mu$ L or
- Toxicities grade  $\geq$  3

Table 3: Recommended Dose Modifications for Toxicities during V-MAC in expansion and maintenance

Event	Occurrence	Action
Non-Hematologic Toxicities		
Grade 3 or 4 non-hematologic toxicities	1 st occurrence	Interrupt venetoclax. Once the toxicity has resolved to Grade 1 or baseline level, venetoclax therapy may be resumed at the same dose. No dose modification is required.
	2 nd and subsequent occurrences	Interrupt venetoclax. Follow dose reduction guidelines in Table 4 when resuming treatment with venetoclax after event has resolved to grade 1.

Hematologic Toxicities (only during maintenance)		
Grade 3 or 4 neutropenia with infection or fever; or Grade 4 hematologic toxicities (except lymphopenia)	1 st occurrence	Interrupt venetoclax.  To reduce the infection risks associated with neutropenia, granulocyte-colony stimulating factor (G-CSF) may be administered with venetoclax if clinically indicated.  Once the toxicity has resolved to Grade 1 or level on day 1 of maintenance, venetoclax therapy may be resumed at the same dose.
	2 nd and subsequent occurrences	Interrupt venetoclax. Consider using G-CSF as clinically indicated. Follow dose reduction guidelines in Table 4 when resuming treatment with venetoclax after event has resolved to Grade 1 or on day 1 of maintenance.

Table 4: Dose Modification for Toxicity during Venetoclax Treatment

Dose at interruption, mg	Restart dose, mg
400	300
300	200
200	100
100	50
50	Stop study drug permanently

Table 5: Dose Modification for Toxicity during Venetoclax Treatment in case of **Co-medication with strong CYP3A inhibitors**

Dose at interruption, mg	Restart dose, mg
100	50
50	20
20	10

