##### **8.1.5.4 Laboratory parameters**

Laboratory parameters will be analyzed descriptively and separately for each time point. Additionally the parameters will be classified as “normal” / “abnormal, not clinically significant” / “abnormal, clinically significant” and change tables will be calculated comparing V1 with V8–EOT.

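### For maintenance patients the only laboratory change comparison reaching into maintenance starts at V1, in active leukemia, so it cannot separate the maintenance effect from remission

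*Protocol*

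**What the plan says.** The laboratory analysis for phase II is in Protocol 8.2.7.3, which refers back to 8.1.5.4 for phase I. That section plans two things. First, "Laboratory parameters will be analyzed descriptively and separately for each time point". Second, values are put into three classes (normal, abnormal without clinical significance, abnormal with clinical significance), and "change tables will be calculated comparing V1 with V8–EOT". Section 8.2.7.3 then adds one sentence: "Additionally a comparison of V1 and EOT is done for patients who received more than one treatment cycle".

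The time points are fixed elsewhere. On V1, section 5.4.1 says "Day 1 of venetoclax will define the study treatment start", and Table 9 places V1 on that day. On disease state at V1, patients have relapsed AML or, in phase II, may be "Primary refractory after 1-2 cycles of standard induction chemotherapy". On entry to maintenance, section 5.4.3 names "Patients who achieve a CR/CRp with ANC recovery", with ANC of at least 1 x 10^9/L, for up to twelve 28-day cycles. Table 10 schedules a full blood count and chemistry on cycle 1 day 1, on day 15, at the end of cycles 2, 4, 6, 9 and 12, and at premature end of study.

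**The concern.** A laboratory change table for a treatment phase is useful when its reference value is taken just before that phase. Here the reference lies one whole phase earlier. Between V1 and the end of maintenance the patient has received V-MAC, gone through aplasia and reached remission, and only then started continuous venetoclax. For a value that active leukemia had made abnormal, remission moves it one way and maintenance toxicity can move it the other. The V1-to-EOT change is the sum of the two.

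At stake is a clear view of laboratory tolerability during continuous dosing. Section 1.4 gives exploration of that mode of use as one reason for the trial, and section 1.3.2 lists neutropenia as an identified risk of venetoclax. A reader of the change table alone could take loss of counts on maintenance for stability or gain.

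**Working it through.** The point rests on no stated figure, so there is no plan figure to reproduce. The check is a reading of the text followed by an illustration.

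**1. Who is covered.** Section 5.1.2 describes the site supply as "sufficient for one full cycle of V-MAC for one patient", and Table 1 gives one V-MAC course. Section 5.4.3 is the only source of further cycles. The added sentence in 8.2.7.3 therefore covers the maintenance patients.

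**2. What EOT must mean.** If EOT meant V8, the added comparison would repeat the V1-to-V8 comparison already taken over from 8.1.5.4. It must mean the end of maintenance, which agrees with Table 11, where EOT is the end of cycle 12. The label is not used consistently, however: 8.1.5.4 joins it to V8, and Table 10 calls the cycle 12 visit EOS.

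**3. Which change comparisons exist.** There are two: V1 to V8, and V1 to EOT. Neither starts at V8, at the maintenance pre-visit or at maintenance cycle 1 day 1. Only the second reaches into maintenance. The two together do not supply the missing one. The V1-to-V8 table is not restricted to maintenance patients. Even in the same patients, two shift tables sharing V1 do not give the joint distribution of V8 and EOT, which is what shows who worsened.

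**4. One patient, assumed values.** ANC 0.4 at V1, 2.5 at maintenance day 1 and 0.9 x 10^9/L at EOT.
- Planned change: 0.9 - 0.4 = +0.5.
- Change over maintenance: 0.9 - 2.5 = -1.6.
- The EOT value is below the 1000/µL level that section 5.4.4 uses as a maintenance trigger. If both 0.4 and 0.9 are classed as clinically significant, the V1-based table shows no shift.

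**5. Shift table, assumed shares.** Let q be the share abnormal at V1. Let t be the share abnormal at EOT, all patients being taken as normal at maintenance day 1. Take the two as independent. The protocol gives neither value.
- Worsening seen from maintenance day 1: t.
- Worsening seen from V1: t(1 - q).
- Improvement seen from V1: q(1 - t).
- Shown as unchanged although worsened on maintenance: tq.
- Net worsening seen from V1: t(1 - q) - q(1 - t) = t - q.

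| t | q | Worsening from V1 | Improvement from V1 | Net worsening from V1 |
|---|---|---|---|---|
| 20% | 30% | 14% | 24% | -10% |
| 20% | 50% | 10% | 40% | -30% |
| 20% | 70% | 6% | 56% | -50% |
| 20% | 90% | 2% | 72% | -70% |
| 40% | 30% | 28% | 18% | +10% |
| 40% | 50% | 20% | 30% | -10% |
| 40% | 70% | 12% | 42% | -30% |
| 40% | 90% | 4% | 54% | -50% |

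The V1-based table shows the fraction 1 - q of the true shifts: 70% at q = 30%, down to 10% at q = 90%. It shows net worsening only when t exceeds q.

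**The case against.** The strongest reply is that the laboratory analysis does not consist of this one comparison. Values are summarized at every time point, so a fall from 2.5 to 0.9 would be visible in the maintenance visits. Adverse events are recorded until 28 days after the last venetoclax dose and tabulated by CTCAE grade and by relation to venetoclax. Exposure and interruptions are reported. Section 8.2.3.2 defines the tolerability endpoint by adverse events, not by laboratory shifts. All of this stands. A reader might infer that maintenance toxicity would be hidden from the safety analysis as a whole, and the documents do not support that. Two limits remain. Summaries by time point describe groups, not within-patient change. And under section 7.1.1 a laboratory value judged not clinically significant is not an adverse event, nor is a finding no worse than a baseline that the section does not define for maintenance.

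A reader might also see a contradiction with Table 3, which for hematologic toxicity on maintenance says "Once the toxicity has resolved to Grade 1 or level on day 1 of maintenance". That is one of two alternative conditions for resuming drug, not a statistical baseline. It shows that the level at maintenance entry has meaning in the protocol, but it contradicts nothing in 8.2.7.3.

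Nor is V1 to EOT wrong in itself. It is a legitimate summary of the whole treatment, so calling for its removal goes too far. It is also not always favourable: EOT may coincide with relapse, when counts may again be leukemic. For the same reason, a table starting at maintenance day 1 would not isolate a pure drug effect. It would only remove the V-MAC and remission step.

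Finally, the choice of reference for a descriptive table is often left to the SAP. Here the protocol did not leave it open. It named V1, so the point concerns a stated choice and not a missing detail.

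**Conclusion.** The point holds in a limited form. For maintenance patients, the only planned laboratory change comparison that extends into maintenance starts in active leukemia before V-MAC, and none starts at maintenance entry, although the data for one are collected. Deterioration on maintenance can therefore appear as no change or improvement in that table.

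The effect mainly concerns blood counts, LDH and uric acid. Among the counts, platelets are affected less uniformly, because CRp allows them to stay at or below 100,000/µL at maintenance entry. Liver and kidney values are restricted at study entry, so they are less affected.

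The size cannot be derived from the documents. The range of 70% down to 10% of true shifts visible rests on assumed shares abnormal at V1, on independence, and on all patients being normal at maintenance day 1. The analysis is descriptive and applies to a subgroup, those in CR/CRp without another post-remission option. The primary endpoint and sample size are not affected. This is a worthwhile, inexpensive improvement, not a defect that threatens the trial's conclusions.

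**What to change.** In 8.2.7.3, for patients who start maintenance, add a change table from maintenance cycle 1 day 1 (Table 10) to (a) the worst value or CTCAE grade during maintenance and (b) the end of maintenance, meaning the end of cycle 12 or premature end of study. Keep V1 to V8 for the V-MAC phase and V1 to EOT as a whole-treatment supplement.

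In the same edit, state which visit EOT means, and use one label in 8.1.5.4, 8.2.7.3, Table 10 and Table 11.

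The cost is one more descriptive table and a few words. Every value needed is already scheduled. The change should be made before database lock, because section 8.3 treats analyses that were not pre-specified and are run after lock as additional or exploratory.
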